6.13 Wash-out Period for Eligibility

If a subject is receiving treatment with another experimental drug, this subject requires a 3-month wash-out period before participating in the screening visit.

6.14 Treatment Compliance

[...]

7 STUDY PROCEDURES

[...]

7.9 Study Duration

The overall duration of the study will be approximately 36 months as indicated below:

- Administrative and ethical procedures: 6 months
- Duration of subject enrolment: 12 months
- Study drug administration: 24 weeks/subject
- Follow-up period: 24 weeks/subject
- Close-out monitoring visits and statistical analysis: 4 months
- Final report and data publication: 2 months

Project's Gantt

[figure not shown]

Table 2. SCHEDULE OF PROCEDURES

		Treatment Period								Follow-up Period		End of study (only for drop outs)
		Randomization – baseline Day 1	Weeks 1 - 3	Week 4	Weeks 5 - 11	Week 12	Weeks 13-23	Week 24	Week 36	Week 48		
Screening (-28 days)	Screening (-28 days)											
Informed consent	x											
Patient's numbering assignment	x											
Date of visit	x	x	x	x	x	x	x	x	x	x	x	x
Demographic data	x											
Blood sample collection (biomarkers)		x		x		x		x		x		x
Personal and clinical data	x											
Physical exam	x	x										
Neurological exam	x	x		x		x		x	x	x	x	x
Medical history/ Concomitant medical disorders	x	x										
Concomitant medications	x	x	x	x	x	x	x	x	x	x	x	x
Inclusion/exclusion criteria	x	x*										
Randomization		x										
Study drug infusion		x	x	x	x	x	x					
Study drug management for nebulization		x	x	x	x	x	x	x				x
Study drug dispensing		x	x	x	x	x	x					
Vital signs, weight	x	x	x	x	x	x	x	x	x	x	x	x
Height	x	x										
ALSFRS-R scale	x	x		x		x		x	x	x	x	x
FVC	x	x		x		x		x	x	x	x	x
ALSAQ-40 scale		x						x		x		x

Clinical lab tests**	x	x		x		x		x		x		x
Pregnancy test		x						x				x
Compliance check (nebulization)			x	x	x	x	x	x				x
AE assessment		x	x	x	x	x	x	x	x	x	x	x
Reason of discontinuation												x

* Certain eligibility criteria are assessed at Day 1, prior to randomization

** According to the physician judgment. Clinical lab test needed for inclusion criteria could be valid if performed up to 6 months before randomization visit

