4.2 Inclusion Criteria

- 1) Age 18 through 80 years inclusive;

- 2) Geographically accessible to the site and able to come to the site center once a week for 24 weeks;
- 3) “Definite” or “Probable” or “Probable laboratory-supported” ALS diagnosis according to the revised El Escorial criteria;
- 4) Disease duration 6 to 24 months from symptom onset to study entry;
- 5) Self sufficiency: Satisfactory bulbar and spinal function (score 3+ on the ALSFRS-R for swallowing, cutting food and handling utensils, and walking);
- 6) Satisfactory respiratory function (FVC \geq 80% of predicted);
- 7) Documented progression of symptoms in the last three months as measured by the ALSFRS-R scale (decrease of at least one point);
- 8) Ability to understand and comply with the study requirements;
- 9) Ability to give written informed consent personally or, as an alternative, via a legally authorized representative;
- 10) Treatment with riluzole 50 mg twice/day for at least 1 month prior to screening visit;

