4.3 Exclusion Criteria

- 1) History of HIV, clinically significant chronic hepatitis, antecedent polio infection, or other active infection;
- 2) Motor neuron disease (MND) other than ALS;
- 3) Involvement of other systems possibly determining a functional impairment (as measured by the end-points) for the entire duration of the study;
- 4) Other severe clinical conditions (e.g., cardiovascular disorders, neoplasms) with impact on survival or functional disability in the next 12 months;
- 5) Renal insufficiency as defined by a serum creatinine $>$ 1.5 times the upper limit of normal
- 6) Poor compliance with previous treatments;
- 7) Other experimental treatments in the preceding 3 months prior to screening visit;
- 8) Women who are lactating or able to become pregnant (e.g. who are not post menopausal, surgically sterile, or using inadequate birth control) and men unable to practice contraception for the duration of the treatment and 3 months after its completion;
- 9) Unwillingness or inability to take riluzole;
- 10) Poor compliance with an inhalation device;
- 11) Abnormal liver function defined as AST and/or ALT $>$ 3 times the upper limit of the normal.

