6 STUDY TREATMENTS

6.1 Study Drug Administration

RNS60 or placebo supply will be sent to site by ALMAC group and should be kept refrigerated in the Hospital Pharmacy with access limited to those directly involved in the study.

RNS60 or placebo will be administered weekly intravenously (starting on Day 1) at the clinic site by properly trained staff designated by the investigator. Subjects will receive 375 mL RNS60 or placebo infused at a rate of 700 mL/hr. Infusion documentation should include recording infusion start and stop times, volume infused, and any interruptions to the infusion using an ad-hoc form.

During the remaining days of the week, treatment with nebulized RNS60 or placebo will be performed at home in the morning on non-infusion days. The subject will remove the kit box of 2 syringes from refrigeration, and visually inspect the syringe to ensure that the plunger and tip cap have remained intact during storage. If either the plunger or the tip cap is loose, the faulty syringe shall be set aside and returned to study staff on the next infusion. Any faulty syringes will be sent back to Revalesio for investigation. Subjects will receive a number of syringes that will guarantee a sufficient number of doses between visits. To dispense a syringe, subjects should first remove the tip cap of the syringe, then gently push the plunger down to dispense the full 2 mL of RNS60/placebo from the syringe into the nebulizer dosing cup. The procedure is then repeated with a second syringe to get to the full daily dose of 4 mL. The dose should be nebulized immediately thereafter until the contents of the nebulizer cup are empty (approximately 15 minutes). Subjects should try to dose at a similar time each morning. Subjects will be provided with and trained to use a Pari Mini system and LC Sprint nebulizers (Italian subjects) or Pari Trek system and LC Sprint nebulizers (US patients). Dosing records for nebulization will be completed at home at the time of each daily nebulization. The dosing record will include the date and time of nebulization as well as the number of syringes used.

All subjects will concurrently take 50-mg riluzole twice a day during the entire treatment period. According to the European Medicine Agency (EMA) guidelines, riluzole can be discontinued when the plasma transaminase levels exceed by fivefold the baseline levels.

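### Footnote ** to Table 2 lets AST/ALT and creatinine results up to 6 months old decide exclusions 5 and 11, so a current exceedance that nobody has recognised can pass entry

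*Combined protocol and SAP*

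**What the plan says.** Table 2 (section 7.9) ticks clinical laboratory tests at screening, on Day 1 and at later visits, and attaches footnote ** to the whole row. The footnote has two parts. The first makes the tests discretionary: "According to the physician judgment". The second sets the permitted age of a result used for entry: "Clinical lab test needed for inclusion criteria could be valid if performed up to 6 months before randomization visit".

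The limits that such a result would serve are in section 4.3. Exclusion 5 begins "Renal insufficiency as defined by a serum creatinine" and sets the limit at 1.5 times the upper limit of normal. Exclusion 11 begins "Abnormal liver function defined as AST and/or ALT" and sets it at 3 times the upper limit. Neither says when the sample must be taken.

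Two other entries bear on timing. Inclusion 10 (section 4.2) requires "Treatment with riluzole 50 mg twice/day for at least 1 month prior to screening visit", and Table 2 places screening within the 28 days before Day 1. Footnote * adds: "Certain eligibility criteria are assessed at Day 1, prior to randomization". It does not name those criteria.

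**The concern.** Exclusions 5 and 11 are meant to keep out patients who have renal insufficiency or abnormal liver function when they enter. A result several months old shows only that the patient was within limits then. If the value has since risen above the limit and no newer test was done, the patient can be randomized without any breach of the written rule.

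For AST/ALT there is a further point. Every participant takes riluzole, and section 6.1 itself ties riluzole discontinuation to transaminase levels. A sample drawn before riluzole was started says nothing about liver function on it. An exceedance found only after randomization is also more awkward than one found before. Under section 6.11, stopping riluzole during treatment stops the study drug, and withdrawn patients are not replaced.

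**Working it through.** No sample size, power or error rate enters this point, and the plan states no figure to reproduce. The check is a reading of the text followed by date arithmetic.

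**Which criteria the footnote covers.** The footnote speaks of inclusion criteria, but none of the ten in section 4.2 uses a blood-chemistry value. The numeric blood-chemistry limits are exclusions 5 and 11. The allowance would have little purpose if it did not reach them, though it may also cover other tests.

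**Whether anything visible forces a fresh result.**
- The screening and Day 1 ticks for clinical laboratory tests carry the discretionary footnote, so they do not make a test mandatory.
- Footnote * covers unnamed criteria only.
- The withdrawal rule for abnormal laboratory values (section 6.11) acts only after entry.

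**Date arithmetic.** Inputs:
- Maximum age of a result: 6 months (footnote **), taken as 182.6 days.
- Screening window: 28 days (Table 2).
- Minimum riluzole before screening: 1 month (inclusion 10), taken as 30 days.

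Results:
1. Permitted age relative to the screening window: 182.6 / 28 = 6.5.
2. Minimum riluzole exposure at randomization = 30 days + time from screening to Day 1. This runs from 30 + 0 = 30 days to 30 + 28 = 58 days.
3. Time by which the oldest accepted result predates riluzole, at that minimum exposure = 182.6 − exposure. This runs from 182.6 − 58 = 124.6 days to 182.6 − 30 = 152.6 days, or about 125 to 153 days (4.1 to 5.0 months).
4. The gap in step 3 shrinks as riluzole exposure lengthens and is zero once exposure reaches 6 months. Longer-treated patients are unaffected by the riluzole part, but their result can still be 6 months out of date.

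**Whether a 28-day limit would close the gap.** A sample drawn at the screening visit or later follows at least 30 days of riluzole. Even one drawn 28 days before randomization, in a patient screened on the day of randomization, follows at least 30 − 28 = 2 days of it. A 28-day limit therefore puts every entry AST/ALT on riluzole without a separate condition.

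**The case against.** The strongest reply is that the footnote is permissive. It allows an old result without requiring one, and it does not override exclusions 5 and 11. A patient known or suspected to exceed a limit is still excluded. Table 2 ticks laboratory tests at screening and on Day 1, and has the eligibility criteria checked at both. A site that draws those tests and reads them before dosing has a current value. This stands, and it narrows the point to exceedances that nobody has recognised in patients for whom the physician relied on an older result. It does not remove the point, because the written rule permits exactly that.

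Second, sections 7.1 to 7.8 are cut from the public text and may require fresh screening tests. This cannot be ruled out. A stricter rule there would, however, conflict with the footnote, which would still need correcting.

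Third, little risk specific to this trial is shown. RNS60 is oxygenated saline with no chemical active ingredient (section 1.5), the toxicology in section 1.3 found no target-organ toxicity, and patients are already on riluzole before screening. This stands and keeps the point minor. A reader might infer renal harm from the infusion schedule ("Subjects will receive 375 mL RNS60 or placebo infused at a rate of 700 mL/hr", weekly). The documents do not support that: each infusion is small, and for creatinine the argument is only that the protocol's own limit should hold at entry.

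The timing of FVC and ALSFRS-R might also be held up as a standard. Both are trial endpoints measured at every main visit, so their schedule says little about how recent safety chemistry needs to be.

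**Conclusion.** The point holds as a minor eligibility-safety gap. Results up to about 183 days old may decide exclusions 5 and 11, with fresh tests left to judgment. A patient with an unrecognised current exceedance can be enrolled within the rules. At the minimum riluzole exposure, the accepted AST/ALT can predate riluzole by about 125 to 153 days. This rests on reading the footnote as covering exclusions 5 and 11, on months of 30 and half-years of 182.6 days, and on the cut parts of section 7 not adding a mandatory test.

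Three stronger readings are not supported:
- A reader might infer that some number of the 142 patients would enter above a limit. The documents give neither a rate of abnormal results nor the frequency with which old ones would be used, so no count can be computed.
- A reader might set the 6-month allowance against inclusion 4 ("Disease duration 6 to 24 months from symptom onset to study entry") and infer that a result could date from symptom onset. That is a corner case at the lower limit, and disease duration is not shown to bear on AST/ALT or creatinine.
- A reader might infer that the fivefold transaminase rule in section 6.1 or the trial results are compromised. Nothing here shows that, and sample size, power and the analyses in section 11.2 are unaffected.

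**What to change.** Add one clause to footnote **, after the 6-month allowance: *except that AST, ALT and serum creatinine used for exclusions 5 and 11 must be measured within 28 days before randomization and reviewed before the first dose.* Keep the 6-month allowance for any other eligibility test it may cover, so that no other test loses its stated window. Sections 6.1 and 11.2 need no change. If the unpublished parts of section 7 already require this, the clause simply brings the footnote into line.

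This is a cheap improvement. It costs at most one routine draw per patient, at a screening visit where laboratory tests are already ticked, and possibly a few more screen failures. The number of failures cannot be estimated from the documents.

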7 STUDY ADMINISTRATION

8.1 Resource Utilization

[...]

8.2 Regulatory and Ethical Compliance

This study was planned and shall be performed according to the principles of Good Clinical Practice (ICH-GCP), the declaration of Helsinki, and the national laws and regulations about clinical studies. The study will not start without written approval of an Independent Ethics Committee (IEC) and the written informed consent of the patients. This study was designed and shall be implemented and reported in accordance with the protocol.

8.3 Responsibilities of the Investigator and IRB/IEC/REB

[...]

8.4 Informed Consent

Eligible patients can be included in the study only after proving written the IRB/IEC/REB - approved informed consent, or, if incapable of doing so, after such consent has been provided by a legally acceptable representative. In cases where the patient's representative gives consent, the patient should be informed about the study to the extent possible given his/her understanding. The physician will obtain a signed informed consent form (ICF) from the subject prior to any procedures. The signed and completed ICF will be accessible in the patient's records on site. A copy of the signed ICF will be given to each subject.

The process of obtaining informed consent should be documented in the patient source documents.

Women of child bearing potential should be informed that taking the study treatment may involve unknown risks to the fetus if pregnancy were to occur during the study and agree that in order to participate in the study they must adhere to the contraception requirement for the duration of the study.

8.5 Amendments to the Protocol

Any change or addition to the protocol can only be made in a written protocol amendment. Only amendments that are required for patient safety may be implemented prior to IRB/IEC/REB approval in accordance with the Italian legislation. Notwithstanding the need for approval of formal protocol amendments, the investigator is expected to take any immediate action required for the safety of any patient included in this study, even if this action represents a deviation from the

protocol. In accordance with the GCP rules and the Italian legislation, the acceptance of an amendment of the study protocol by each participating institution is subjected to the local IRB/IEC/REB approval or notification.

8.6 Publication of Study Results

The results of the study will be published whether or not the experimental drug is considered superior to placebo.

9 SAFETY MONITORING

Safety monitoring for all patients enrolled in the study will include laboratory safety assessments and clinical evaluations, as shown in Table 2. All AEs and SAEs will be recorded. Subject diaries about AEs and/or concomitant medication will not be copied but will be considered source documents. AE documentation by the investigator will include the date of onset and duration of the AE, as well as the severity and causality of each AE, and the actions taken, including the discontinuation of the experimental drug, where required.

9.1 Emergency Unblinding of Treatment Assignment

[...]

9.2 Adverse Events

The Investigator is responsible for recording all AEs observed during the study.

For expected (listed) AEs of RNS60, see the current version of the IB.

All AEs will be collected starting from the signing of informed consent through the infusion visits and the follow up. During this period the investigator is responsible for reporting to the sponsor all non-serious AEs, SAEs occurring in subjects treated by the investigator in the clinical trial.

AEs (but not SAEs) occurring before starting study treatment but after signing the informed consent form are recorded on the Medical History/Current Medical Conditions Case Report Form.

[...]

Investigators must code the grade of all AEs occurring during the trial. For more detail about grade criteria, refer to “Common Terminology Criteria for Adverse Events (CTCAE)” Version 4.0 Published: May 28, 2009 (v4.03: June 14, 2010) from the U.S. DEPARTMENT OF HEALTH AND HUMAN SERVICES National Institutes of Health National Cancer Institute.

9.3 AE Reporting

All AEs, regardless of severity and whether or not they occurred during the treatment or follow-up period, are to be recorded on the appropriate AE pages in the e-CRF. The investigator will include the date of onset and duration of the AE, as well as the severity and causality of each AE, and the actions taken. Each event should be recorded separately.

[...]

In case of patients needing a Non Invasive Ventilation (NIV), it is necessary to record the procedure into the AE form.

The investigator shall report all AEs and DAEs into the e-CRF, without reporting to “Mario Negri” IRCCS.

9.4 Reporting of SAEs and SUSARs

[...]

The following serious events should not be recorded as SAE due to the usual progression of the disease and the investigator judgment:

- Death (only if caused by the disease progression);
- Tracheotomy;
- PEG/RIG placement.

If these events occur, the Investigator must record them into the AE form.

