2.2 Secondary Objectives

1. The preliminary efficacy of RNS60 on functional disability, as measured by the ALSFRS-R scale;
2. The preliminary efficacy of RNS60 in prolonging survival (or time to tracheostomy, whichever comes first);
3. The preliminary efficacy of RNS60 in slowing the decline of forced vital capacity (FVC) from baseline;
4. The tolerability and safety of RNS60 through the identification of unexpected adverse events;
5. The impact of RNS60 on quality of life as measured by ALSAQ-40 scale.

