2.4 Secondary Endpoints

1. The mean change in the proportion of T-reg (measured via FOXP3 and CD25 mRNA); the mean change over time in the plasma concentrations of Cyp-A, 3-NT, Actin-NT, MCP-1, IL-17 during the follow up period (from 24 to 48 weeks);
2. The cumulative proportion of subjects becoming no longer self-sufficient at 4, 12, 24, 36 and 48 weeks in the two treatment arms (defined as those scoring 2 or lower on at least one of the ALSFRS-R items for swallowing, cutting food and handling utensils, or walking);
3. The mean change of ALSFRS-R total score in the two treatment arms during the treatment and follow up period;
4. The cumulative proportion of deaths or tracheostomies in the two treatment arms during the entire study including follow-up;
5. The mean change of FVC score in the two treatment arms during the treatment and follow up period;
6. The total number of subjects in the two treatment arms experiencing at least one AE leading to treatment discontinuation at 4, 12 and 24 weeks;
7. The mean number of AEs per treatment arm at 4, 12, 24 and 48 weeks;

8. The mean change of ALSAQ-40 score measuring quality of life at the completion of the treatment and follow up period.

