The numerical change of FVC, ALSFRS-R and ALSAQ-40 during the treatment and follow-up period will be assessed using repeated measures ANOVA, with an unspecified variance covariance matrix. The hypothesis will be tested using the time*treatment interaction which measures differences in the slope of the ALSFRS-R. Survival (time to death or tracheostomy) and time to functional disability (i.e., to reach a non self-supporting status or death or tracheostomy) will be assessed using actuarial methods with death and non-self supporting status as end-points. Survival will be described with the Kaplan-Meier method. Differences between the two treatment groups will be compared using the log-rank test. The statistical significance will be set at the 0.05 level for a two-tailed test.

The repeated measures ANOVA will use all available data, using Maximum Likelihood methods as suggested by (<http://www.nap.edu/read/12955/chapter/1>).

Safety analysis will be performed in all subjects receiving at least one dose of the experimental drug. All AEs, SAEs and AEs leading to treatment discontinuation will be recorded, listed and compared in the two treatment arms at any follow-up visit and at the end of the study. The number of patients reporting at least one AE or SAE will be compared between the treatment arms using the fisher exact test. The total number of AE and SAE will be compared between the treatment arms using a poisson model. MedDRA code system will be used for all recorded AE/SAE.

Given the exploratory value of this study, multiple comparison adjustments for Type I errors will not be considered as a more conservative significance level would lead to miss any potential treatment effect. Furthermore, if there is a suggestive benefit ($p<0.1$) in the clinical measures and several of the biomarkers, this will be considered sufficient evidence for further study.

If at the end of the patient enrolment period less than 50% of patients are enrolled, an interim-analysis will be performed to decide whether or not to continue the trial.

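### The planned AE comparisons count ALS progression events as adverse events, so slower progression on RNS60 could dilute or offset an excess of other AEs

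*Combined protocol and SAP*

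**What the plan says.** Section 9.4 lists death caused by disease progression, tracheotomy and PEG/RIG placement under the rule "The following serious events should not be recorded as SAE due to the usual progression of the disease and the investigator judgment". It then instructs: "If these events occur, the Investigator must record them into the AE form". Section 9.3 adds NIV: "In case of patients needing a Non Invasive Ventilation (NIV), it is necessary to record the procedure into the AE form".

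The safety objective in Section 2.2 (item 4) is "The tolerability and safety of RNS60 through the identification of unexpected adverse events". The matching count endpoint in Section 2.4 (item 7) is "The mean number of AEs per treatment arm at 4, 12, 24 and 48 weeks". Section 11.2 gives two tests: "The total number of AE and SAE will be compared between the treatment arms using a poisson model" and "The number of patients reporting at least one AE or SAE will be compared between the treatment arms using the fisher exact test". Neither section visibly excludes, flags or separately tabulates the progression events.

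Death and tracheostomy are also an efficacy outcome, item 4 of Section 2.4: "The cumulative proportion of deaths or tracheostomies in the two treatment arms during the entire study including follow-up". PEG/RIG and NIV are not listed as endpoints.

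**The concern.** The plan treats three of these events as the normal course of ALS when it defines SAEs, but the AE analysis does not carry that distinction through. On the visible text, the AE total is therefore a sum of two quantities: events that may reflect tolerability, and milestones of the disease that the drug is meant to slow. A death or tracheostomy enters once on the efficacy side and once on the safety side.

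At stake is how the pre-specified AE comparison is read. A near-equal AE count could mean that RNS60 is well tolerated. It could also mean that extra treatment-related events were balanced by fewer progression entries. The planned tests cannot tell these apart. If the separation is chosen only after unblinding, it becomes a post-hoc decision.

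**Working it through.** The documents state no AE rate, progression-event rate or power for the safety endpoint, so there is no plan figure to reproduce.

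**Inputs from the documents.** 71 patients per arm (Section 3), a two-sided 0.05 level (Section 11.2), and a targeted 43% slowing of ALSFRS decline over 6 months (Section 11.1).

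**Assumptions.** *b* = other AEs per placebo patient; *d* = progression entries per placebo patient; *R* = true active/placebo ratio for other AEs; *P* = the ratio for progression entries. *P* = 0.57 carries the 43% over to event counts. That is an assumption, because the 43% is a slope figure over 6 months while events are counted to 48 weeks, half of that time off treatment. *P* = 0.75 and *P* = 1.00 are shown for range.

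**Observed AE ratio** = (*bR* + *dP*) / (*b* + *d*). With *R* = 1.25:

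| *b* | *d* | *P* = 1.00 | *P* = 0.75 | *P* = 0.57 |
|---|---|---|---|---|
| 4 | 0.2 | 1.24 | 1.23 | 1.22 |
| 2 | 0.5 | 1.20 | 1.15 | 1.11 |
| 1 | 0.5 | 1.17 | 1.08 | 1.02 |
| 1 | 1.0 | 1.13 | 1.00 | 0.91 |

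First row, last column: (4 × 1.25 + 0.2 × 0.57) / 4.2 = 5.114 / 4.2 = 1.22. Last row, last column: (1.25 + 0.57) / 2 = 0.91. These rows illustrate the effect and do not bound it.

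**Full offset** occurs when *b*(*R* − 1) = *d*(1 − *P*), that is *d*/*b* = (*R* − 1)/(1 − *P*). At *P* = 0.57 this is 0.25/0.43 = 0.58 for *R* = 1.25, and 0.50/0.43 = 1.16 for *R* = 1.50.

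**Events.** The shortfall on RNS60 is *d* × 0.43 × 71: 6.1 entries at *d* = 0.2 and 15.3 at *d* = 0.5.

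**Effect on the Poisson test.** Let *m*P and *m*A be the mean AEs per patient on placebo and RNS60. SE = √(1/(71 *m*P) + 1/(71 *m*A)), and power = Φ(ln(*m*A/*m*P)/SE − 1.96), with no overdispersion.

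- *b* = 1, *R* = 1.50, progression entries removed: means 1 and 1.5, SE 0.153, ln 1.5 = 0.405, power 75%.
- The same with *d* = 0.5 and *P* = 0.57: means 1.5 and 1.785, ratio 1.19, SE 0.131, power 26%.
- *b* = 4, *d* = 0.2, *R* = 1.25, *P* = 0.57: power falls only from 80% to 71%.

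**No effect on progression** (*P* = 1, *b* = 1, *d* = 0.5, *R* = 1.50): the ratio is (1.5 + 0.5)/1.5 = 1.33 instead of 1.50. The difference in means is 2.0 − 1.5 = 0.5, the same as 1.5 − 1.0. Power falls from 75% to 61%.

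**No difference in other AEs** (*R* = 1, *P* = 0.57): the ratio is 4.114/4.2 = 0.98 at *b* = 4, *d* = 0.2, and 1.57/2 = 0.785 at *b* = *d* = 1. The drug then looks better tolerated than it is relative to placebo.

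**Fisher test.** A progression entry changes a patient's status only if that patient has no other AE. If other AEs were Poisson, that share on placebo would be e^(−*b*): 37% at *b* = 1 and 2% at *b* = 4.

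**The case against.** **The AE definition is not visible.** Parts of Sections 9.2 to 9.4 are omitted from the public text. The visible sentences say where to record these events, not that every entry is an analysed AE, and NIV is called a procedure. A rule could sit in the missing text. This stands as a caveat. An exclusion from analysis would belong in Section 11.2, however, and the visible safety paragraph there has none.

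**Side effects are not hidden.** A reader might infer that the rule masks RNS60's side effects, or that endpoint 7 cannot serve the safety objective at all. The documents do not support that. Severity and causality are recorded for each event (Section 9.3) and AEs are MedDRA-coded and listed, so an excess of headache, for example, would still show. Three of the four event types are kept out of SAEs, which leaves that comparison largely unaffected. Section 9.3 does not say whether NIV may be an SAE.

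**Not all four are efficacy endpoints.** Only death and tracheostomy are.

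**No benefit does not produce a false rise.** With equal progression in both arms, the mean difference is unchanged. If RNS60 speeded progression, the extra entries would be a real harm signal, though not one of tolerability.

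**Few early events.** Entry requires FVC of at least 80% of predicted and preserved swallowing, utensil and walking scores, so little effect is likely at weeks 4 and 12. On the other side, Section 11.1 expects 85% of placebo patients to lose self-sufficiency by 24 weeks. That makes later progression entries plausible without giving their rate.

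**A counterweight.** Follow-up stops at death or tracheotomy, and no exposure offset is stated. A slower-progressing arm therefore has longer to accrue AEs, which works partly the other way.

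**Inclusive recording is defensible**, because attributing a death to progression is an investigator judgment. This supports keeping the all-entries result, but not as the only one.

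**Conclusion.** The point holds as a limited defect in the pre-specified AE comparisons. On the visible text, the Poisson and any-AE comparisons mix tolerability with disease progression. Whenever progression entries have a lower ratio than other AEs, including them lowers the observed AE ratio. The follow-up-time effect runs partly against this, so the net bias is not settled.

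The size depends on the ratio of progression entries to other AEs, which the documents do not give. Under the assumed rates it runs from negligible (1.25 seen as 1.22) to a reversal (1.25 seen as 0.91). The supported conclusion is dilution and possible offset, not concealment of side effects and not an unusable endpoint. The endpoint is secondary in a trial that calls itself exploratory, but the correction is cheap and should be made before unblinding.

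**What to change.** Leave site reporting unchanged, then:

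- Flag NIV, PEG/RIG placement, tracheotomy and progression death on the e-CRF AE page, or identify them by a pre-specified MedDRA term list.
- In Section 2.4 (item 7) and Section 11.2, run the between-arm AE count and any-AE comparisons on AEs excluding these four event types.
- Report the all-entries comparison beside it, so that the result can be checked against the judgment on cause of death.
- Tabulate the four event types separately by arm.
- Include log follow-up time as an offset in the Poisson model.
- If the omitted text of Sections 9.2 to 9.4 already settles whether these entries are analysed AEs, cite that rule in Section 11.2.

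The cost is SAP wording, one flag or term list, and one more table.
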